When the brain is given a stimulus, through the eyes or ears, it emits a responsive electrical charge, called a Cortical Evoked Response. These electrical responses, measured via electrodes, travel throughout the brain and is ultimately perceived as vision and audible sound. When the input stimulus resembles a pattern the brain itself uses, the brain responds by synchronizing to it, a process called Frequency Following Response (FFR). The Sana Mask utilizes this above described AVS mechanism to induce FFR. The firmware consists of periods of light/sound pulsing at three distinct pulse frequencies; ~8Hz, 3Hz, and 1Hz. For each frequency, there are distinct sections where the audio and visual pulses vary from eye to eye, and ear to ear.

The website for the device can be found here: <https://www.sana.io/>

Previous Trials Using the Sana PR:

The Sana Pain Reliever device has been in a previous study entitled "Photic Sleep Enhancement During a Mars Analog Exploratory Mission Simulation" that received a Western Institutional Review Board Certificate of Approval (attached). Two abstracts from studies involving the device are also attached.

2. Objectives

Primary: Determine the effectiveness of the Sana PR at reducing chronic pain over an 8-week intervention period and the long-lasting effect of pain relief at a 4-week follow-up using the following outcome measures:

Secondary Objectives:

- 1) Determine the impact using the device for an 8-week intervention has on Quality of Life and Sleep
- 2) At both baseline visits and both follow-up visits participants will complete a body chart on pen and paper to draw out where they feel their pain. Changes to the location of their pain will be measured.
- 3) Determine the tolerability and user acceptability of the devices

3. Device

The Sana Pain Reliever (Sana PR) by Sana Health Inc is a device comprised of one (1) main component (Mask with Earbuds) and two (2) ancillary components (Charger and Headband). The device is worn over the eyes (with earbuds in ears). The device pulses light at a single wavelength but various frequencies throughout a specific firmware algorithm. Through the earbuds, the device also plays different tones in conjunction with the pulses. The device has a skin contacting Heart Rate Variability (HRV) sensor built into the forehead area that measures HRV throughout use.

Figure 1: the Sana mask

4. Study Procedures

Description of the Study Design

Design:

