SECOND BASELINE CLINICAL ASSESSMENT (Week 2) - AT THE ARC OR VIA VIDEO CALL

Participant Information will be collected including:

- Record of changes in medications
- Record of changes in pain management techniques participants typically used
- Documentation of the location of their pain on a body chart

Participants will then complete the following questionnaires:

- Neuropathic Pain Symptom Inventory (NPSI)
- Pittsburgh Sleep Quality Index (PSQI)
- Beck Depression Inventory (BDI)

- Patient health Questionnaire Type 9 for Depression (PHQ-9)
- General Anxiety Disorder 7-item questionnaire (GAD-7)
- World Health Organization Quality of Life BREF (WHOQOL-BREF) & World Health Organization Quality of Life Pain (WHOQOL-pain)

Study Devices: Participants will be randomized into the Sham or Real study group arm and will undergo a Sana PR familiarization session:

ARM 1: Real

- Participants will be loaned a Sana PR device, headphones, charging cables and a strap to secure the device on their head
- The research team will download the Sana Health application on a tablet device compatible with the application that will be loaned to participants (this device will be a tablet that has all functions not necessary to the functionality of the Sana application disabled). The device will be loaned to participants for the duration of the 8-week intervention.
- The research team will teach the participant how to use the Sana PR device and the Sana Health application.

Participants will be given an instruction manual for the device and mobile application. Participants will be instructed to call the lab's direct phone-line [contact] if they have any additional questions when using the device at home.

- Participants will then complete their first 15 min session with the device in its normal settings under the supervision of the research team. For the Real arm, the session with the devices consists of periods of light/sound pulsing at three distinct pulse frequencies; ~8Hz, 3Hz, and 1Hz. For each frequency, there are distinct sections where the audio and visual pulses vary from eye to eye, and ear to ear. This first session will ensure the subjects know how to properly use the devices and that there are not any adverse events (AEs) from the first use of the device. Participants will be instructed to call the lab's direct phone-line [contact] if they experience an AE when using the device at home.

ARM 2: Sham

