- Participants will be loaned a Sana PR device, earplugs, a charging cable and a strap to secure the device on their head
- The research team will download the Sana Health application on a tablet device compatible with the application that will be loaned to participants (this device will be a tablet that has all functions not necessary to the functionality of the Sana application disabled). The device will be loaned to participants for the duration of the 8-week intervention.
- The research team will teach the participant how to use the Sana PR device and the Sana Health application. Participants will be given an instruction manual for the device and mobile application.

Participants will be instructed to call the lab's direct phone-line [contact] if they have any additional questions when using the device at home.

- Participants will then complete their first 15 min session under the supervision of the research team. For the Sham arm, the device will have the light on for 5 min, off for 5 min and then on again for 5 min. Ear plugs will be used in place of headphones. There will be no sound from the device in the sham group. This familiarity session will ensure the subjects know how to properly use the devices and that there are not

any adverse events (AEs) from the first use of the device. Participants will be instructed to call the lab's direct phone-line [contact] if they experience an AE when using the device at home.

Safety monitoring: A member of the research team will call the participant 48 hours after the first session with device to check for AEs, difficulties using the device and answer any questions.

INTERVENTION (Week 2 - 10) - AT THE HOMES OF THE PARTICIPANTS

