Devices: Participants will be instructed to use the Sana PR every time they experience pain during the day (ad libitum). There will be no minimum or maximum number of uses. Participants will open the Sana Health application and will be prompted to answer the amount of pain they are feeling in the moment using the VAS on the Sana Health application. If it is the first time the participant is using the device for the day, they will also be prompted by the application to complete a VAS to report on how they slept the evening prior. Participants will then turn on the devices using the application. Participants will complete a 15-min cycle with the device. Participants may complete multiple, sequential uses of the device without requiring them to interface with the application. Participants will be prompted to answer the amount of pain they are feeling in the moment after using the VAS on the Sana Health application.

Participants will also be asked to use the Sana PR device every evening immediately prior to/accompanying falling asleep for the night. Participants will open the Sana Health application and will be prompted to answer the amount of pain they are feeling in the moment using the VAS on the Sana Health application. Participants will then be prompted as to what medication they took for their pain that day. The application will be populated with the medications participants reported at the first baseline visit.

Participants will select from this list of medications. Participants will complete a 15 min cycle with the device.

Every two weeks during the 8-week intervention period participants will receive a message on their cellular devices via text message to complete the NPSI, PSQI, PHQ-9 and GAD-7. Participants will be sent compliance reminders to complete these questionnaires on their phones and on the tablet.

Safety monitoring: Participants will be instructed to contact the research team to report any AE over this period. Compliance will be monitored over the 8 week intervention period. A significant decrease in the compliance during (responding to less than 70% of the last 10 scheduled check-ins) of using the device the 8 week intervention will be considered an indication that a participant may need assistance. A research team member will call the participant to ensure that the reason of the drop in usage of the device is not due to an AE.

POST INTERVENTION FOLLOW UP (Week 10) - AT THE ARC OR VIA VIDEO CALL Participant

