We will use mixed modelling to determine the effect of the intervention on reported chronic pain – our primary outcome variable. We will also use ANOVAs (or their non-parametric equivalents) to assess changes in all of our outcome measures; including pain scores, sleep scores, device usage statistics, medication usage, heart rate variability, blood pressure, and quality of life measures.

6. Safety Assessment

Participants will be monitored for possible AEs throughout the study according to the frequency of the data review below. Participants will be given the email and phone number of the research team to report AE and circumstance of events. Participants will be reminded during the familiarization session with the device, at the second baseline visit, to seek immediate medical attention should they experience an injury as a result of being in the study. This will also be reiterated to participants if they reach out to report an AE. Data from the Sana Health application will be used to track compliance. Significant decrease in the compliance during (responding to less than 70% of the last 10 scheduled check-ins) of using the device the 8 week intervention will be considered an indication that a participant may need assistance. A research team member will call the participant to ensure that the reason of the drop in usage of the device is not due to an AE. Any AEs that occurs will be reported to the IRB to see if risk/benefit ratio is still acceptable for each individual participant and for the continuation of the study as a whole.

7. Benefits

Although no benefits can be guaranteed, it is possible that subject will experience a reduction in amount of chronic pain that they typically experience.

While there is no guarantee that this study will be beneficial to society, we hope that this study will help lead to the development of a device that can help reduce chronic pain and provide individuals who experience chronic pain with an alternative solution for managing pain.

8. Payment and Remuneration

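### For the 54 days between the 48-hour call and the week 10 visit, no adverse event question is scheduled for all participants, and the only staff call about events goes to low compliers

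*Combined protocol and SAP*

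**What the plan says.** Section 4 (Study Procedures) gives both arms the same AE schedule. The first session at the week 2 visit is supervised, partly to check for AEs from first use. Then "A member of the research team will call the participant 48 hours after the first session with device to check for AEs". Participants are asked about AEs at the week 10 visit and again at week 14.

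Between the 48-hour call and week 10, under "INTERVENTION (Week 2 - 10) - AT THE HOMES OF THE PARTICIPANTS", the protocol has two routes. One is participant-initiated: "Safety monitoring: Participants will be instructed to contact the research team to report any AE over this period", with a similar instruction at the familiarization session ("Participants will be instructed to call the lab's direct phone-line [contact] if they experience an AE when using the device at home"). The other is a compliance trigger, defined as "responding to less than 70% of the last 10 scheduled check-ins". When it is met, staff ask whether an AE is the cause: "A research team member will call the participant to ensure that the reason of the drop in usage of the device is not due to" (the quotation stops just before the AE is named). Section 6 repeats both routes. It adds that AEs go to the IRB, which considers whether risk/benefit remains acceptable for the individual and for the study.

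The app collects pain and sleep VAS ratings and medication use. Every two weeks it also prompts for the NPSI, PSQI, PHQ-9 and GAD-7, with reminders. None of these is described as an AE question.

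Secondary objective 3 is "Determine the tolerability and user acceptability of the devices". AEs are missing from the list of data to be collected in Section 4. Section 5 plans ANOVAs to "assess changes in all of our outcome measures; including pain scores, sleep scores, device usage statistics, medication usage" and several other measures, and names neither AEs nor tolerability.

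**The concern.** Two things are at stake.

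The first is timeliness. Use has no upper or lower limit, and for almost eight weeks nobody asks a compliant participant whether anything has gone wrong. An event that the participant does not think worth a phone call is first elicited at week 10. By then the mask is being returned and the app no longer runs it, so the event cannot inform that participant's exposure or the risk/benefit review while treatment continues.

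The second is evenness of capture. The one active route during treatment reaches only people who stop answering check-ins. The arms receive quite different experiences: pulsed light with sound, or steady on/off light with earplugs. Compliance may therefore differ. If it does, one arm is questioned more often than the other, and part of any AE difference could reflect how events were found.

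**Working it through.** The documents give no figure for AE capture, so there is none to reproduce. The check has three steps.

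**1. The interval.** Weeks 2 to 10 are (10 − 2) × 7 = 56 days. The 48-hour call is day 2 and the week 10 visit is day 56, so the interval is 56 − 2 = 54 days. This uses only the protocol's own schedule.

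**2. How strongly the extra call depends on compliance.** Under 70% of 10 means 6 or fewer answered. The protocol does not define a scheduled check-in. I assume one per day for 56 days, answered independently with probability p. The single-window figure is the binomial probability P(X ≤ 6) with n = 10. The ever-triggered figure comes from simulating 20,000 participants at each p.

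| Adherence p | Triggered in one window | Ever triggered in 56 days (T) |
|---|---|---|
| 90% | 1.3% | 15.8% |
| 80% | 12.1% | 74.6% |
| 70% | 35.0% | 97.8% |

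Under these assumptions, a fall in adherence from 90% to 80% raises the share ever called from about one in six to about three in four.

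**3. What that could do to AE counts.** Every input here is assumed: a true AE risk of 20% in both arms; spontaneous reporting s; week 10 recall r, applied to everyone; 90% detection on a triggered call; independent routes; adherence of 90% in one arm and 80% in the other. The captured share is

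C = 1 − (1 − s)(1 − r)(1 − 0.9T).

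The spurious difference in points is therefore

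20 × (1 − s)(1 − r) × 0.9 × (0.746 − 0.158) = 20 × (1 − s)(1 − r) × 0.529.

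| Week 10 recall r | s = 30% | s = 50% |
|---|---|---|
| 50% | 3.7 | 2.6 |
| 80% | 1.5 | 1.1 |
| 95% | 0.4 | 0.3 |

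For example, with s = 30% and r = 50%: 20 × 0.7 × 0.5 × 0.529 = 3.7 points (recorded risks 14.0% and 17.7%). Setting r = 0 would give 7.4 and 5.3 points, but that ignores the week 10 question and so does not describe this plan. If adherence is equal, the two values of T are equal and the difference is zero. The formula also credits the call with events that occur after it, so it leans towards overstatement.

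**The case against.** A reader might infer that the arms cannot be compared fairly on tolerability, or that AE capture as a whole depends on adherence. The documents do not support either reading. The schedule and the trigger are the same in both arms. Everyone is asked about AEs at weeks 10 and 14 whatever their compliance, and volunteered reports do not pass through the trigger. Bias between arms needs differing compliance and incomplete recall together, and the documents give no data on either. If 180 participants were split equally (the allocation ratio is not stated), the standard error of a between-arm difference near 15% would be √(2 × 0.15 × 0.85 / 90) = 5.3 points, larger than any entry in the second table.

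A reader might also infer that a safety signal would go unseen for nearly all of the exposure. That is too strong. Participants have a phone line and email contact and are told to seek immediate care for an injury. The fortnightly scales track pain, sleep, mood and anxiety in both arms. Section 6 refers to a data review frequency that the available text does not give, so periodic review cannot be ruled out. Such a review can, however, see only events that someone has reported.

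Three further objections stand in part:

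- Tolerability is more than AE counts. The Human Factors Questionnaire, the ease-of-use questions and device usage all bear on objective 3.
- The outcome list in Section 5 is introduced as non-exhaustive, and the visits plainly collect AEs, so their absence from the data list is a drafting gap. Even so, no AE comparison is specified anywhere.
- An app question is answered only by those who use the app, so it cannot replace the compliance call. That call is a sensible safeguard for people who stop because of an AE.

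**Conclusion.** The point holds in this form. For 54 of the 56 home-treatment days, AE information rests on volunteered reports, on recall at week 10, and on a call that only low compliers receive. The interval follows directly from the protocol and needs no assumption. So does the consequence that an event not volunteered may surface only at device return, after the in-treatment risk/benefit review could have used it.

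Uneven capture between arms is a possibility, not a finding. With the assumed inputs above it ranges from 0.3 to 3.7 points, and it is zero if compliance is equal. Those figures show only how the mechanism works; the documents cannot tell us its size or direction. Separately, the plan specifies no AE analysis for an objective that names tolerability. This is a worthwhile and inexpensive improvement, and it does not invalidate the comparison.

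**What to change.** - Add one fixed AE question to the existing fortnightly app questionnaire, worded identically in both arms: any new or worse symptom since the last prompt, when it began, and whether it is still present. Send positive answers to the research team. If prompts fall at about days 14, 28, 42 and 56, the longest interval between scheduled questions becomes about 14 days for those who respond.
- Keep the compliance call, the week 10 and week 14 questions and spontaneous reporting.
- Add AEs to the list of data collected in Section 4, with the source of each event (app item, spontaneous, compliance call, visit). Define a scheduled check-in, and state the data review frequency to which Section 6 refers.
- In Section 5, compare by arm the number of participants with any AE from all sources combined. Add a sensitivity analysis that excludes events found only through compliance calls. Do not make that exclusion the main analysis, because it would drop events in people who stopped because of an AE. Per-session rates should be descriptive only, since ad libitum use is a post-randomisation variable.

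The cost is a small edit to an app that is subject to InfoSec review, one table by arm with its sensitivity analysis, more minor events on record, and some extra follow-up calls.

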Information will be collected including:

- Record of changes in medications
- Record of changes in pain management techniques participants typically used
- Documentation of the location of their pain on a body chart

Participants will then complete the following questionnaires:

- Neuropathic Pain Symptom Inventory (NPSI)
- Pittsburgh Sleep Quality Index (PSQI)
- Beck Depression Inventory (BDI)
- Patient health Questionnaire Type 9 for Depression (PHQ-9)
- General Anxiety Disorder 7-item questionnaire (GAD-7)
- World Health Organization Quality of Life Bref (WHOQOL-BREF) & World Health Organization Quality of Life Pain (WHOQOL-pain)
- Patient's Global Impression of Change (PGIC)
- Human Factors Questionnaire

- Responses to questions on ease of device use and the likelihood they would hypothetically continue using the devices in their daily life.

Devices: Participants will be asked to return the Sana PR mask at this visit. The application will stop working to control the device at the end of the 8-week intervention and will not let participants to continue using the Sana PR device.

Safety monitoring: Participants will be asked to report any AEs.

CONTINUED PAIN MONITORING BETWEEN FOLLOW UP VISITS (Week 10 – Week 14) - AT THE HOMES OF THE PARTICIPANTS

Participants will be asked to use the tablet with the Sana application daily, at night prior to going to sleep. Participants will be asked to complete a VAS of how they slept the night prior, a VAS of their amount of pain and asked to report the medications they used that day for pain management.

4 WEEK FOLLOW UP VISIT (WEEK 14) - AT THE ARC OR VIA VIDEO CALL Participant information will be collected including:

- Record of changes in medications
- Record of changes in pain management techniques participants typically used - Documentation of the location of their pain on a body chart

Participants will then complete the following questionnaires:

- Neuropathic Pain Symptom Inventory (NPSI)
- Pittsburgh Sleep Quality Index (PSQI)
- Beck Depression Inventory (BDI)
- Patient health Questionnaire Type 9 for Depression (PHQ-9)
- General Anxiety Disorder 7-item questionnaire (GAD-7)
- World Health Organization Quality of Life Bref (WHOQOL-BREF) & World Health Organization Quality of Life Pain (WHOQOL-pain)
- Patient's Global Impression of Change (PGIC)
- Human Factors Questionnaire

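### Device acceptability questions and the PGIC are asked only at weeks 10 and 14, so the questionnaire part of the acceptability objective is missing for anyone who leaves the study before week 10

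*Combined protocol and SAP*

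**What the plan says.** All references are to the combined protocol and SAP.

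- **Objective.** Section 2 (Objectives) lists as its third secondary objective: "Determine the tolerability and user acceptability of the devices". It names no instrument, time point or analysis population.
- **Acceptability items.** In section 4 (Study Procedures), the week 10 visit lists the "Human Factors Questionnaire" and "Responses to questions on ease of device use and the likelihood they would hypothetically continue using the devices in their daily life". The week 14 visit repeats both. The PGIC is listed at the same two visits and no others.
- **During the intervention (weeks 2 to 10).** Participants are prompted every two weeks "via text message to complete the NPSI, PSQI, PHQ-9 and GAD-7". No acceptability item and no PGIC is in that set.
- **Other contacts and data before week 10.** The first session is supervised. Staff then "call the participant 48 hours after the first session with device to check for AEs, difficulties using the device". For the rest of the period, "Participants will be instructed to contact the research team to report any AE over this period". If a participant answers fewer than 70% of the latest ten check-ins, staff call "to ensure that the reason of the drop in usage of the device is not due to an AE". The app time-stamps every session.
- **Early exit.** No early-termination visit, exit questionnaire or reason-for-stopping record is described.
- **Analysis.** Section 5 (Data Analysis plan) names device usage among its outcomes. It does not name acceptability or the PGIC, and it gives no analysis population and no rule for missing answers.

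**The concern.** A participant who leaves because the mask is uncomfortable, inconvenient or unhelpful has given the kind of answer that objective 3 is looking for. Under the schedule as written, that person never reaches the questions. The missing answers are then plausibly related to what the answers would have been, and a summary of week 10 responses describes only those still attending.

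The comparison between arms could suffer too. The real device gives pulsing light and tones. The sham gives light on, off and on again, with earplugs and no sound. Users may leave the two arms at different rates, in which case equal acceptability among attenders need not mean equal acceptability among those randomised.

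A smaller issue affects people who stop using the mask but stay in the study. Someone who stops in week 3 and attends week 10 does answer, but from recall 10 − 3 = 7 weeks later.

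**Working it through.** **Step 1: who can answer, and when.**

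| Source | When | Covers people who leave before week 10? |
|---|---|---|
| Human Factors Questionnaire, ease-of-use and continued-use items | Weeks 10 and 14 | No |
| PGIC | Weeks 10 and 14 | No |
| Fortnightly app questionnaires | Weeks 2 to 10 | Yes, until exit, but with no acceptability item |
| Supervised first session | Week 2 | Yes (adverse events, correct use) |
| 48-hour call | Two days after first session | Yes (adverse events, difficulty of use) |
| Adverse event reports | Throughout | Yes, until exit |
| Low-compliance call | When triggered | Yes, if triggered; stated purpose is to rule out an adverse event |
| Time-stamped sessions | Weeks 2 to 10 | Yes, including date of last use, but no reason |

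The gap is therefore in the questionnaire items. The tolerability sources do reach people who later leave.

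**Step 2: size, as an illustration only.** The plan states no figure for acceptability or dropout, so there is none to reproduce. The one figure available is the enrolment goal of 180 (section 4, Subjects), treated here as the number randomised.

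Assumptions, none from the documents:
- d = share leaving before week 10: 5%, 10%, 20% or 30%
- p = acceptability among those who answer: 80%
- q = acceptability among leavers: 0% or 40%

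Number answering = 180 × (1 − d).
All-randomised acceptability = (1 − d)p + dq.
Overstatement = p − [(1 − d)p + dq] = d(p − q).

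| d | Number answering | All-randomised, q = 0% | Overstatement | All-randomised, q = 40% | Overstatement |
|---|---|---|---|---|---|
| 5% | 171 | 76% | 4 points | 78% | 2 points |
| 10% | 162 | 72% | 8 points | 76% | 4 points |
| 20% | 144 | 64% | 16 points | 72% | 8 points |
| 30% | 126 | 56% | 24 points | 68% | 12 points |

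The formula also shows when the problem disappears. If q = p the overstatement is zero, and if q exceeds p the sign reverses. With no assumption about leavers at all, the all-randomised figure lies between (1 − d)p and (1 − d)p + d. For d = 20% that is 0.8 × 80% = 64% to 64% + 20% = 84%.

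**Step 3: unequal loss between arms.** Keep p = 80% in both arms and q = 0%, and let 20% leave the real arm and 10% the sham arm. Attenders show 80% v 80%. The all-randomised figures are 0.8 × 80% = 64% and 0.9 × 80% = 72%, a difference of 8 points that the questionnaire answers alone would not show. The direction of unequal loss is arbitrary here; the documents do not suggest one.

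**The case against.** The strongest objection is that much of objective 3 is covered by other data. The supervised session, the 48-hour call, adverse event reporting, the low-compliance call and the usage log all collect information before a later departure, and usage is named for analysis. A reader might infer from the visit schedule that the whole tolerability objective is judged on those who stayed. The documents do not support that, and this part of the objection stands in full.

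Further points on the same side:

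- **Stopping the mask is not leaving the study.** Daytime use is as needed with no minimum, nothing requires withdrawal for non-use, week 10 can be done by video, and each follow-up visit carries a $50 payment. People who stop using the mask may well still answer. This stands, and it limits the gap to people who leave the study altogether, a number the documents do not give.
- **The stopping date is not lost.** The app logs each session, so last use is known. This stands; only the reason is unrecorded.
- **The low-compliance call may capture more than adverse events.** The plan treats low compliance as a sign that help may be needed, so the caller may hear other reasons. This stands in part: nothing says that those reasons are recorded.
- **The PGIC is not tied to objective 3.** This stands. It shares the timing gap but should not be counted as an acceptability measure.
- **Unequal loss would not be invisible.** Attendance and usage by arm would reveal it. This stands, provided they are reported beside the acceptability result, which the plan does not commit to.
- **Asking after the full eight weeks is a reasonable choice.** Exit answers reflect shorter exposure. This stands as a reason to show them separately, but not as a reason to leave them uncollected.

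The other data do not fill the gap completely. The 48-hour call comes too early to explain later abandonment, adverse event reports do not capture dislike, and falling as-needed use could mean relief as easily as rejection.

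**Conclusion.** The point holds for the questionnaire-based acceptability part of objective 3 and, separately, for the PGIC. Both will be missing for participants who leave before week 10, and the acceptability result is likely to be too favourable if leavers like the device less. That condition is plausible but not established by the documents.

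The size of any bias cannot be computed from the plan. The range of 2 to 24 points rests wholly on the assumed rates in the working, and the bias is near zero if few people leave or if leavers think much as stayers do. As written, the plan has no questionnaire data from leavers with which to check the second possibility.

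The matter concerns one secondary objective, and this point raises no question about the primary pain outcome. It is a cheap improvement, best made before or during enrolment, because the answers cannot be reliably recovered once people have left.

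**What to change.** 1. When a participant withdraws or stops using the mask, ask the existing acceptability questions and the PGIC at that point, on the tablet or during the low-compliance call already planned.
2. Record the main reason for stopping. The date of last use is already in the app log.
3. In the Data Analysis plan, state which measures serve objective 3 (questionnaires, adverse events, staff calls, usage) and in which population each is summarised.
4. Report discontinuation, reasons and usage by arm for all randomised participants, beside the week 10 acceptability figure.
5. Add a sensitivity analysis that counts participants who left because of the device as not willing to continue. This is one imputation choice, so it should accompany the observed figure and not replace it.
6. Show early-exit answers separately from week 10 answers, since they reflect shorter exposure.

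**Cost.** A small amendment using existing questionnaires, the existing tablet and an existing call. It takes a few minutes per early stopper. Some will decline, so the gap will shrink without closing, and the reported acceptability may be less favourable.
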